3.0 STUDY DESIGN

[figure not shown]
This study will be a randomized clinical trial involving a total of 24 subjects. We propose to recruit subjects into 2 groups: 1) Extraction treated with xenograft bone substitute (BioOss Collagen®) + collagen dressing (HeliPlug®), 2) Extraction treated with xenograft bone substitute (BioOss Collagen®) + 3D-collagen matrix (Mucograft Seal®). All subjects recruited will have already been approved and treatment planned for extraction + implant placement by non-study personnel to avoid any potential conflict of interest. All subjects will have radiographs that show the tooth planned for extraction. Each subject will be eligible for only 1 tooth extraction + dental implant rehabilitation. After tooth extraction, subjects will receive a standard site preservation therapy consisted with xenograft bone substitute + collagen dressing or the alternative site preservation therapy consisted with xenograft bone substitute + 3D-collagen matrix. After the conventional 6-month healing period, subjects will receive a dental implant in the previous extracted site. During the dental implant procedure, a 2x5mm bone core biopsy + a 2mm gingival biopsy will be obtained from the implant site.

Biopsy samples will be stored for future histological and histochemical analysis. After dental implant placement, all subjects will receive a healing abutment for soft tissue healing prior to implant restoration.

During the 6-month healing time after tooth extraction and site preservation therapy, subjects will return at week-1, week-2, week-4, month-3, and month-6 for intra-oral scanning for soft tissue volumetric acquirement. Subjects will receive a Cone beam computed tomography (CBCT) prior to extraction for the baseline hard-tissue volume measurement and appropriate extraction planning and at 6-month post-extraction for volumetric measurement and appropriate implant treatment planning.

Hard tissue analysis will be performed to compare linear ridge remodeling (baseline vs. 6-month healing). CBCT images will be analyzed by non-contact reverse engineering system (Geomagic software). Soft tissue volumetric analysis will be performed to compare the soft tissue healing between BioOss Collagen + Mucograft Seal and BioOss Collagen + Collagen Dressing. Images captured with an intra-oral scanner (Trios, 3Shape) collected at baseline, week-1, -2, -4, month-3, and month-6.

Figure 2. Surface analysis representation from baseline and month-6 post-extraction with blue surface representing the loss of hard-tissue after tooth extraction.

3.1 MASKING

This study will be conducted in a single masked manner such that all volumetric assessments will be performed without knowledge of the subjects' type of treatment.

3.2 RANDOMIZATION

Qualified subjects will be assigned randomly into one of two groups: 12 subjects into the xenograft + 3D-collagen group (Test) and 12 subjects into the xenograft + collagen dressing group (Control).

The study coordinator will place 24 identically sized slips of paper, 12 reading "Test" and 12 reading "Control", into a sealed envelope. The study coordinator will select one sealed envelope for each qualified subject, and record the randomization results and staple the slip of paper into the subject study folder.

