4.4 SUBJECT IDENTIFICATION

At screening, participants will be assigned a 3-digit counter/screening number by the study center (001, 002, etc.). At treatment baseline/series, each subject will receive a unique 4-digit study number (1001, 1002, etc.) that will identify their group status in the study. Participants who do not complete the study will be replaced until 24 participants have completed the study.

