5.1 PRE-SCREENING EXAMINATION

Subjects will contact the study coordinator by telephone for information regarding participation in the study. Study coordinator/assistant will perform a brief telephone interview to determine whether or not the patient will qualify based on age and basic inclusion and exclusion criteria. Study coordinator/assistant will read a list of basic inclusion and exclusion criteria to potential subjects and ask potential subjects if they believe they would qualify. Subjects indicating they may qualify would be scheduled for a screening examination appointment.

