5.2 VISIT 1: SCREENING EXAMINATION

Study personnel will provide each study candidate with a written informed consent form at the initial visit prior to administration of any research related treatment. Prior to enrolling a subject, study personnel will explain to each subject the protocol, procedures and objectives of the study, and the patient's role in the study, before obtaining consent. Subjects will be given the opportunity to read the informed consent document. Study personnel will answer all questions that the subject may have and ensure that the subject understood all aspects of the study. When the subject understands and is willing to participate in the clinical trial, he/she must sign and date the Institutional Review Board (IRB) approved Informed Consent Form.

This screening visit will consist of the following procedures:

- All subjects will complete a medical health history questionnaire.
- The reason for extraction of the hopeless tooth will be documented (caries, periodontal disease, infection, fracture, resorption).
- Full mouth clinical measurements including probing pocket depth (PPD), clinical attachment level (CAL), bleeding on probing (BOP) and gingival index (GI) will be performed on all teeth.
- Standardized cone beam computed tomography (CBCT) will be taken.
- 3Shape Trios scanner will be used to make a digital impression of the maxillary arch. This will be used for surgical planning, volumetric measurements, and to fabricate surgical guides for implant placement.

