7.0 STATISTICAL ANALYSIS

Descriptive statistics (means and standard deviations for continuous variables and frequencies for categorical variables) will be produced for vital signs, demographic characteristics, medical history and clinical variables, both overall, and for each of the two groups of study participants. Summaries of clinical variables will be presented at baseline and at study exit. Adverse events (including onset, duration, treatment, outcome and suspected causality) and reasons for withdrawals will be listed and summarized.

A power analysis was performed using a statistical power calculator (SAS Power Procedure, Cary, NC). This study will have a sample size of 24 subjects, 12 in each of the two groups. We will have at least 90% power (with a Type I error rate of 5%) to detect a difference of 2.5mm in the horizontal ridge width measured at 3mm below the most coronal aspect of the crest, assuming a standard deviation of 1.6mm, as determined by a previous study (Jung, Philipp et al. 2013). This power calculation takes into account the estimated 10% of subjects drop out. A “p” value of less than 0.05 will be considered statistically significant.

For soft tissue analysis, the primary outcome was the within-participant difference between the linear and volume changes at the test and control groups. These differences were measured in each participant prior to surgery, as well as 3 and 6 months after surgery, leading to a series of three longitudinal differences for each participant. For each group, the differences at all three time points were analyzed simultaneously using a linear mixed model (LMM), in which the actual linear and volume measures were modeled as a function of time (categorical), treatment group, and the interaction of time and treatment, while accounting for the repeated measures on each participant with a random participant effect. Given that both time and treatment are categorical, our approach was a generalized version of repeated measures ANOVA, as our LMM allowed for differing variability in linear and volume measures at each time point. Within each LMM, we also tested for a difference between the two treatment groups with respect to the overall time pattern in linear and volume measures. Due to the exploratory nature of the analysis, no Bonferroni correction for multiple testing was applied. Statistical significance was defined as a p -value < 0.05 .

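### The coordinator who shares in pre-screening also prepares, draws and records a fixed pool of 24 slips, and no allocation method exists for replacement subjects

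*Combined protocol and SAP*

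**What the plan says.** All references are to the combined protocol and SAP.

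- **Section 3.2 (Randomization), preparation.** "The study coordinator will place 24 identically sized slips of paper". Twelve slips are marked for each arm, and all are said to go into one sealed envelope.
- **Section 3.2, drawing and recording.** "The study coordinator will select one sealed envelope for each qualified subject", and the coordinator is then to "record the randomization results and staple the slip of paper into the subject study folder". No independent preparer, numbering, opacity or order of opening is described.
- **Section 5.1 (Pre-screening).** "Study coordinator/assistant will perform a brief telephone interview to determine whether or not the patient will qualify". Section 5.2 then gives the in-person screening visit and consent to unspecified staff: "Study personnel will provide each study candidate with a written informed consent form at the initial visit".
- **Section 4.4 (Subject Identification).** "Participants who do not complete the study will be replaced until 24 participants have completed the study". How a replacement is allocated is not stated here or elsewhere.
- **Section 7.0 (Statistical Analysis).** The sample size is 24, 12 per group. "This power calculation takes into account the estimated 10% of subjects drop out".
- **Section 3.1 (Masking).** Only the volumetric assessments are described as masked.

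**The concern.** Concealment matters most when the staff who treat a subject know the treatment given. Here the two arms use different covering materials and suturing (section 5.3), so past assignments are visible to the team. The only masking described covers volumetric assessment, while the powered outcome is a linear ridge width. Some entry decisions also involve judgement, such as a hopeless prognosis or adequate periodontal health (section 4.1).

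If a person with a part in entry can foresee the next assignment, the choice of whom to schedule, and when, can differ between arms. With 12 per arm, a few such choices can move a mean, and no analysis can repair that afterwards.

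The second problem is supply. A pool of exactly 24 slips is paired with a rule that continues enrolment until 24 subjects complete. Once one subject is lost after allocation, the plan needs an assignment for which it provides neither a slip nor a rule.

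**Working it through.** **1. Reproduce the plan's own figure.** Inputs from section 7.0: difference 2.5 mm, SD 1.6 mm, two-sided 0.05, two-sample equal-variance t-test, power at least 90%, drop-out 10%.

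- Power by noncentral t is 87.5% at 9 per group, 91.0% at 10 and 95.5% at 12, so 10 per group are needed.
- Allowing for drop-out: 10/0.90 = 11.1, rounded up to 12 per group, or 24 in total. The stated figure reproduces.
- If 24 are allocated and 10% are lost, 24 × 0.90 = 21.6 remain. With 11 and 10 analysed, power is 92.4%.

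**2. Allocations implied by the replacement rule.** Section 4.4 requires 24 completers; the drop-out rate d is from section 7.0. Expected allocations = 24/(1 − d).

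| Drop-out | 24/(1 − d) | Rounded up | Beyond 24 slips |
|---|---|---|---|
| 5% | 25.3 | 26 | 2 |
| 10% (stated) | 26.7 | 27 | 3 |
| 15% (assumed) | 28.2 | 29 | 5 |
| 20% (assumed) | 30.0 | 30 | 6 |

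The 5% row is also an assumption. With independent 10% losses, the chance of needing at least one allocation beyond the pool is 1 − 0.9^24 = 92%. The 90% range is 0 to 6 extra (negative binomial, 24 completions). Sections 4.2 and 9.0 also allow exclusion after tooth extraction. If the draw precedes extraction, this could add to the need, but the order is not stated.

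**3. How predictable the 24 slips are to someone with the tally.** Inputs: 12 and 12 slips in random order.

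- Chance that the last k slips are all for one arm, and so known: 2·C(24 − k, 12)/C(24, 12). This gives 100% for k = 1, 47.8% for k = 2, 21.7% for k = 3 and 9.3% for k = 4.
- Expected number of certain assignments: 2 × 12/13 = 1.85 of 24.
- Always guessing the arm with more slips left, with n per arm, gives n + (4^n/C(2n, n) − 1)/2 correct guesses. For n = 12: 12 + (6.204 − 1)/2 = 14.6 of 24, or 60.8%, against 50% if assignments were unpredictable.

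**4. The same guessing measure for possible replacement schemes.**

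- Blocks of 4 (n = 2): 2.83/4 = 70.8%.
- Blocks of 6 (n = 3): 4.10/6 = 68.3%.
- Blocks of 8 (n = 4): 5.33/8 = 66.6%.
- One 15:15 sequence (n = 15): 15 + (6.922 − 1)/2 = 17.96 of 30, or 59.9%.

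Small blocks make guessing from past assignments easier than the present pool does. Guessing the lagging arm in this way does not require knowing the block size.

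**The case against.** The best defence is that this is a small trial with a simple, genuinely random draw, and that safeguards exist. Section 3.0 says that subjects were already approved and planned for extraction and implant by staff outside the study. The pre-screen is a short telephone call that may be done by an assistant, and screening and consent are not assigned to the coordinator by name. Volumetric assessment is masked. Section 7.0 treats 24 as already covering drop-out, so about 27 is a derived figure that the plan does not state. All of this stands, and it narrows the coordinator's discretion. It does not hide the upcoming allocation from the person who prepares, draws and records it.

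Several stronger readings are tempting but unsupported:

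- **That replacement assignments are known in advance, or are not randomised at all.** The documents are silent. Section 4.4 asks for 24 completers in total, not 12 per arm. Filling the short arm is plausible but unwritten, and with losses in both arms even that rule could leave either arm open.
- **That late assignments in general are known.** Only the 24th always is; the last three are all determined in 21.7% of sequences.
- **That the coordinator controls entry.** The text supports a share in telephone pre-screening only.
- **That the envelope procedure cannot work.** Section 3.2 puts all slips in one envelope and then selects an envelope per subject. This is probably a slip of wording for one slip per envelope. It needs correcting but is not evidence of a failed mechanism.

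**Conclusion.** The point holds in this form. One role prepares, draws and records from a fixed 12:12 pool and shares in pre-screening, with no concealment step described. The measurable consequence within the pool is modest: 1.85 certain assignments on average, and 60.8% correct guesses for someone using the tally.

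The larger gap is that the plan's own completion rule and drop-out rate imply about 3 allocations beyond the pool, with a 92% chance of at least one, and no method exists for making them. This rests on reading section 4.4 literally, on the 10% in section 7.0, and on independent losses.

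Sections 4.4 and 7.0 provide for the same losses twice, once by replacement and once by inflation, and must be reconciled. If 24 means allocated with no replacement, the shortage disappears; the lack of concealment remains. The power statement is sound on either reading. The documents give no basis for estimating a bias in millimetres.

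**What to change.** Rewrite section 3.2 as follows.

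- An existing team member with no role in screening, enrolment or surgery prepares a computer-generated 1:1 list of about 30 entries. One 15:15 random sequence, or large blocks of undisclosed size, is suitable; small blocks are not, for the reason in step 4.
- Each allocation goes into its own sequentially numbered, opaque, sealed envelope. The coordinator neither prepares nor sees the list.
- Envelopes are opened strictly in order, and only after eligibility is confirmed. State where this falls relative to the extraction.
- Each replacement takes the next envelope, whichever arm was lost.

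Thirty entries cover 6 replacements, the upper end of the 90% range at 10% drop-out. At 20% drop-out the expected need is already 30, and the upper end of the range is 24 + 11 = 35, so a longer list is prudent if losses of that size are thought possible.

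Then make sections 4.4 and 7.0 agree. Either 24 are allocated and not replaced, which keeps the stated power, or 24 complete and the list is long enough to allow it.

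The cost is protocol wording and a set of envelopes, with no added visits. The downside is that arms may not end at 12:12. For example, opening 27 of a 15:15 list leaves 3 unopened, so the allocated arms differ by 1 or 3. The effect on precision is small: for 24 completers split 14:10, 1/14 + 1/10 = 0.171, against 1/12 + 1/12 = 0.167.

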4.0 HUMAN PARTICIPANTS

The subject population will be 24 adult patients recruited from the general population by means of advertisements and flyers in local media, and from the research patient database. These 24 subjects will be categorized into 2 groups: 1) Extraction treated with xenograft bone substitute (BioOss Collagen®) + collagen dressing (HeliPlug®), 2) Extraction treated with xenograft bone substitute (BioOss Collagen®) + 3D-collagen matrix (Mucograft Seal®). Subjects who require antibiotic prophylaxis prior to dental treatment or those with medical contraindication to dental treatment will be excluded. All study participants will read, have explained by study personnel, and sign a consent form that details the risks, benefits, and requirements for participation in the proposed study.

4.1 INCLUSION CRITERIA

- † Subjects must be adult males or females age 18 to 80 years (inclusive).
- † Subjects must be able and willing to follow study procedures and instructions in English.
- † Subjects must have read, understood and signed an informed consent form in English.
- † Subjects must have a maxillary premolar, canine, lateral incisor, or central incisor with a restorative or periodontal hopeless prognosis (Kwok and Caton 2007), in which an implant is indicated without any sinus lift required.
- † Subjects undergoing implant placement should be in adequate periodontal health prior to implant placement. This includes having probing depth ≤ 4 mm for all remaining teeth at the same quadrant of the proposed implant placement. Patients with periodontal probing sites with probing depths of up to 5 mm may also be included if bleeding on probing in these sites is absent. Each subject should be considered to be periodontally stable prior to the implant surgery.

4.2 EXCLUSION CRITERIA

- † Individuals who have a chronic disease with oral manifestations.
- † Individuals who exhibit gross oral pathology.
- † The use of either antibiotics or chronic use (more than 7 days) of NSAIDs within 1 month prior to screening examination.
- † Individuals that require antibiotic prophylaxis prior to dental treatment.
- † Chronic treatment (i.e. two weeks or more) with any medication known to affect periodontal status (e.g. phenytoin, calcium antagonists, cyclosporine, Coumadin) within 1 month prior to screening examination.
- † Uncontrolled diabetes mellitus (HbA1c >7) within 3 months prior to screening examination.
- † Individual with uncontrolled parafunctional habits, such as clenching and bruxing on objects, that could adversely impact implant survival.
- † Individuals with a history of intravenous bisphosphonates.
- † Individuals with active infectious diseases such as hepatitis, HIV or tuberculosis.
- † Current cigarette smokers.
- † Individuals who are known to be pregnant, breastfeeding or planning to become pregnant within 6 months.
- † Individuals with blood disorders (hemophilia) and /or currently taking anticoagulant medications, such as heparin, warfarin, or clopidrogel.
- † Individuals receiving any therapy known to affect healing, such as high dose corticosteroids, radiation therapy or chemotherapy.
- † Individuals allergic to topical or local anesthesia.
- † Individuals who require maxillary sinus augmentation prior to dental implant therapy.
- † Individuals with dehiscenced, fenestrated, or fractured labial/buccal alveolar bone plate determined after baseline CBCT or after tooth extraction where more than 50% of the buccal bone height is not present. In this case, if the surgeon determines that guided bone regeneration (bone graft and membrane) is needed to repair the defect, it will be done at no cost to the subject, but the subject will be excluded from the study protocol.

4.3 CONTINUANCE CRITERION

There should be no major changes in subjects' medical status during the entire study period for continuation of the protocol. Subjects not meeting this criterion may be withdrawn. Any observed infection around the implant will be reported as an adverse event and subject will be treated and followed until resolved. Clinical judgment of the dental provider will be used to determine presence and severity of undesired healing response. Clinical judgment will also be used when determining whether the dental implant should be removed upon poor healing response and/or infection.

4.4 SUBJECT IDENTIFICATION

At screening, participants will be assigned a 3-digit counter/screening number by the study center (001, 002, etc.). At treatment baseline/series, each subject will receive a unique 4-digit study number (1001, 1002, etc.) that will identify their group status in the study. Participants who do not complete the study will be replaced until 24 participants have completed the study.

4.5 RECRUITMENT

Participants will be recruited by advertisement from the patient, student, and staff population at the University of North Carolina at Chapel Hill. In accordance to UNC HIPPA Research Policy, a request to release PHI (both physical records and electronic records) for the purpose of research may be made to aid in potential participant recruitment. If additional participants are needed, they may be recruited from the general population. We will not recruit participants employed by any of the following UNC School of Dentistry departments: Prosthodontic, Periodontology or GO Health Center.

5.0 SCHEDULE OF PROCEDURES

Periodontally healthy subjects who are eligible and treatment planned for tooth extraction and implant placement will be recruited and examined for this study. Screening and examination procedures may encompass up to 9 outpatient visits over an approximate 8-month period.

5.1 PRE-SCREENING EXAMINATION

Subjects will contact the study coordinator by telephone for information regarding participation in the study. Study coordinator/assistant will perform a brief telephone interview to determine whether or not the patient will qualify based on age and basic inclusion and exclusion criteria. Study coordinator/assistant will read a list of basic inclusion and exclusion criteria to potential subjects and ask potential subjects if they believe they would qualify. Subjects indicating they may qualify would be scheduled for a screening examination appointment.

5.2 VISIT 1: SCREENING EXAMINATION

Study personnel will provide each study candidate with a written informed consent form at the initial visit prior to administration of any research related treatment. Prior to enrolling a subject, study personnel will explain to each subject the protocol, procedures and objectives of the study, and the patient's role in the study, before obtaining consent. Subjects will be given the opportunity to read the informed consent document. Study personnel will answer all questions that the subject may have and ensure that the subject understood all aspects of the study. When the subject understands and is willing to participate in the clinical trial, he/she must sign and date the Institutional Review Board (IRB) approved Informed Consent Form.

This screening visit will consist of the following procedures:

- All subjects will complete a medical health history questionnaire.
- The reason for extraction of the hopeless tooth will be documented (caries, periodontal disease, infection, fracture, resorption).
- Full mouth clinical measurements including probing pocket depth (PPD), clinical attachment level (CAL), bleeding on probing (BOP) and gingival index (GI) will be performed on all teeth.
- Standardized cone beam computed tomography (CBCT) will be taken.
- 3Shape Trios scanner will be used to make a digital impression of the maxillary arch. This will be used for surgical planning, volumetric measurements, and to fabricate surgical guides for implant placement.

